20 MARCH 2019

VERSION 2.0

**PTC THERAPEUTICS, INC.
[name]
[name]**

Notice of Proprietary Information: This document contains confidential information owned by or in the possession/control of PTC Therapeutics, Inc. Except as may otherwise be permitted in writing, by accepting or reviewing these materials, you agree that this information should not be disclosed to others (except where required by applicable law) and should not be used for unauthorized purposes. In the event of an actual or suspected breach of this obligation, PTC Therapeutics, Inc. should be notified promptly.

PROTOCOL SYNOPSIS

Name of Sponsor/Company: PTC Therapeutics
Name of Investigational Product: Ataluren
Title of Study: Phase 2, non-interventional, clinical study to assess dystrophin levels in subjects with nonsense mutation Duchenne muscular dystrophy who have been treated with ataluren for ≥ 9 months.
Study Centers: The study will be performed at a single site at [REDACTED]
Phase of Development: Phase 2
Objectives: Primary: 
To assess the levels of dystrophin in ambulatory nonsense mutation Duchenne muscular dystrophy (nmDMD) subjects currently being treated with ataluren for ≥ 9 months using quantitative electrochemiluminescence (ECL) assay Secondary: 
To assess dystrophin levels/intensity and protein localization by immunohistochemistry Pharmacokinetic: 
To evaluate the steady state pharmacokinetics (PK) of ataluren
Endpoints: Primary: 
Mean dystrophin levels as measured by ECL Secondary: 
Levels and localization of dystrophin protein as determined by immunohistochemistry Pharmacokinetic: 
PK assessments using sparse sampling and population PK modeling in a separate report. The parameters include C_{1/F}, V/F, AUC₀₋₂₄, C_{max}, and C_{ave}.
Study Description and Methodology Single-site, non-interventional study to obtain additional data on the effect of ataluren on dystrophin protein production in nmDMD subjects who currently have been taking ataluren for ≥ 9 months. Quantifying dystrophin levels from nmDMD subject muscle biopsies is challenging due to the difficulty of obtaining muscle samples that contain sufficient amounts of intact muscle cells for analysis. This study has been designed to mitigate these challenges, to the extent possible, by adherence to the following practice parameters: 
Biopsies will be collected from ambulatory nmDMD subjects; a subject population that are more likely to have greater amounts of intact muscle cells compared with older, non-ambulatory patients with nmDMD.A total of no more than approximately 450 mg of muscle tissue (up to [REDACTED] cores per muscle) will be collected from the [REDACTED] and [REDACTED] [REDACTED]. If the [REDACTED] muscle is considered by the investigator to be too small for muscle biopsy sampling, the [REDACTED] [REDACTED] muscle may be used.Two validated, highly sensitive assays, ie, ECL and immunohistochemistry, will be used to measure dystrophin protein levels and to evaluate whether the protein localizes correctly to the muscle membrane.
Study Population: Approximately 6 ataluren-treated subjects with nmDMD.

Main inclusion and exclusion criteria

Inclusion criteria:

1. Evidence of signed and dated informed consent/assent document(s) indicating that the patient (and/or his parent/legal guardian) has been informed of all pertinent aspects of the trial.
2. Male sex.
3. Ambulatory (ie, 10 m walk/run in <30seconds) and functional grade on the Brooke Upper Extremity Scale of a 1 or a 2.
4. Currently being treated with ataluren 10, 10, 20 mg/kg for ≥ 9 months, with no gap in treatment of >1 month prior to study entry.
5. Phenotypic evidence of DMD based on the onset of characteristic clinical symptoms or signs (eg, proximal muscle weakness, waddling gait, and Gowers' maneuver) and an elevated serum creatine kinase (CK). Medical documentation of phenotypic evidence of DMD needs to be provided upon request by the PTC Therapeutics medical monitor.
6. Willing to undergo muscle biopsy.

Exclusion Criteria:

1. Known contra-indication to muscle biopsy (ie, such as bleeding or clotting disorders).
2. Exposure to another investigational drug within 2 months prior to enrollment in the study or ongoing participation in any non-ataluren interventional clinical trial.
3. Requirement for daytime ventilator assistance or any use of invasive mechanical ventilation via tracheostomy. *Note: Evening non-invasive mechanical ventilation such as use of bilevel positive airway pressure (Bi-PAP) therapy is allowed.*
4. Prior or ongoing medical condition (eg, concomitant illness, psychiatric condition, behavioral disorder, alcoholism, drug abuse), medical history, physical findings or laboratory abnormality that, in the Investigator's opinion, could adversely affect the safety of the subject, makes it unlikely that the muscle biopsy or follow-up would be completed, or could impair the assessment of study results.

Statistical analyses:

Dystrophin levels will be summarized using descriptive statistics.

SCHEDULE OF ASSESSMENTS

Study Procedure	Visit 1 ¹	Follow-up (phone call)	Notes
Week (visit window)		Week 1 (± 3days)	
Informed Consent	X		A signed and dated informed consent must be obtained before conducting any study procedures.
Inclusion/Exclusion	X		
Demographics	X		
Medical History	X		
Physical Exam	X		Full physical exam will be performed.
Clinical Labs	X		Biochemistry, hematology, and urinalysis laboratory assessments.
Height/Weight/BMI	X		
Vitals (HR & BP)	X		Vital signs will include systolic and diastolic blood pressure, pulse rate, and body temperature. The pulse rate and blood pressure determinations will be performed with the subject in a sitting position after a 5-minute rest. Blood pressure will be measured in triplicate and the average will be recorded.
Timed function tests	X		Tests include time to climb 4 stairs, time to descend 4 stairs, time to rise from supine, and time to run/walk 10 meters.
PK blood sampling	X		PK samples will be drawn pre-morning dose and 2 hours post-morning dose. Ataluren plasma concentrations will be analyzed in a population PK model for the estimation of key pharmacokinetic parameters including Cl/F, V/F, AUC ₀₋₂₄ , C _{max} , and C _{ave} .
Muscle biopsy	X		Muscle biopsy will be taken from the [REDACTED] and [REDACTED]. If the [REDACTED] muscle is considered by the investigator to be too small for a muscle biopsy sample, the [REDACTED] muscle may be used
AE/SAE Monitoring	X	X	
Concomitant medications	X		Treatments, including ataluren, taken one month prior to enrollment and during Visit 1 will be recorded.

9.3 Protocol Amendment History36
10 REFERENCES.....38

LIST OF TABLES

Table 1. Schedule of Assessments.....22
Table 2. Relationship of Study Muscle Biopsy Procedure to Adverse Event.....26
Table 3. Grading of Adverse Event Severity Grade.....27
Table 4. Investigator Site Requirements for Reporting Adverse Events Not Related to
Muscle Biopsy.....27
Table 5. Investigator Site Requirements for Reporting Muscle Biopsy-Related
Adverse Events.....27

LIST OF ABBREVIATIONS AND DEFINITION OF TERMS

Term	Definition
AE	Adverse event
Bi-PAP	Bilevel positive airway pressure
BMD	Becker muscular dystrophy
BMI	Body mass index
BP	Blood pressure
CK	Creatine kinase
CRF	Case report form
CRO	Contract research organization
CTCAE	Common Terminology Criteria for Adverse Events
DMD	Duchenne muscular dystrophy
EC	Ethics Committee
ECL	Electrochemiluminescence
eCRF	Electronic case report form
FVC	Forced vital capacity
GCP	Good Clinical Practice
HR	Heart rate
ICF	Informed consent form
ICH	International Councilfor Harmonisation
IRB	Institutional Review Board
MedDRA	Medical Dictionary for Regulatory Activities
mRNA	Messenger ribonucleic acid
nmDMD	Nonsense mutation Duchenne muscular dystrophy
PK	Pharmacokinetic
RSI	Reference Safety Information
SAE	Serious adverse event

1 INTRODUCTION

1.1 Disease Background

Duchenne muscular dystrophy (DMD) is a rare, debilitating, progressive, and ultimately fatal childhood disease ([Bushby 2010a](#), [Bushby 2010b](#)). It is an X-linked genetic muscle disorder that results from a mutation in the dystrophin gene. Dystrophin is a 427 kDa structural protein present at the muscle sarcolemma that provides stability to the muscle and is expressed in skeletal, respiratory, and cardiac muscle ([Bushby 2010a](#), [Mah 2016](#), [Rae 2016](#)). It is also expressed in neurons in specific parts of the brain, such as the hippocampus ([Aartsma-Rus 2016](#)).

Dystrophin acts as a shock absorber during muscle contraction by linking the actin of the contractile apparatus to the layer of connective tissue that surrounds each fiber ([Aartsma-Rus 2016](#)). Consequently, dystrophin bears the mechanical stresses that occur during muscle contraction, stabilizing muscle cell membranes, and protecting muscles from injury ([Petrof 1993](#)). Dystrophin mutations disrupt the connection with the actin cytoskeleton and connective tissue resulting in chronic muscle damage, inflammation, and eventually replacement of muscle fibers by fat and fibrotic tissue resulting in progressive and irreversible loss of muscle function ([Muntoni 2003](#)). The culmination of muscle function loss leads to early death; the average life expectancy of DMD patients is about 25 years of age.

Duchenne muscular dystrophy is noticeable in young children, who typically display underdeveloped or delayed development of motor skills relative to healthy boys ([Bushby 2010a](#)). Muscle function continues to deteriorate in pre-adolescence resulting in the loss of gross motor functions, including the ability to rise from the floor, to climb stairs, and to walk. Complete loss of ambulation typically occurs in the early teenage years. Loss of functional abilities occur sequentially, with the loss of one function preceding and predicting the loss of subsequent functions. Importantly, the age at loss of ambulation is predictive of the age of onset of severe respiratory insufficiency (forced vital capacity [FVC] <1 liter) requiring the need for ventilation assistance ([Humbertclaude 2012](#)), which in turn is predictive of death within 3 years ([Phillips 2001](#)).

To date, no medications cure or reverse the effects of DMD. The goals of current interventions are to help slow or stabilize disease progression, prolong patients' ability to manage activities of daily living, and delay the onset of subsequent deterioration. Recent clinical guidelines recommend treatment with glucocorticoids, which address the inflammatory component of the disease, and have beneficial effects on prolonging ambulation and muscle and respiratory function ([Bushby 2010a](#), [Bushby 2010b](#)). Additional treatments are necessary, particularly those that treat the underlying cause of the disease. Because of the role of the dystrophin protein, dystrophin restoration therapy would be expected to stabilize or slow disease progression in patients with DMD.

Approximately 10% to 15% of boys with DMD have the disease due to a nonsense mutation in the dystrophin gene ([Aartsma-Rus 2006](#), [Bladen 2015](#)), resulting in a premature stop codon in the dystrophin mRNA (messenger ribonucleic acid). Consequently, ribosomal

translation of nonsense codon containing mRNA results in premature termination of translation before a full-length, functional protein is generated.

1.2 Ataluren

Ataluren is a small molecule being developed for the treatment of nonsense mutation Duchenne muscular dystrophy (nmDMD). Ataluren promotes ribosomal readthrough of premature stop codons enabling the formation of full-length, functional dystrophin protein (Welch 2007).

The efficacy and safety of ataluren for the treatment of nmDMD were assessed in 2 randomized, double-blind, placebo--controlled, 48-week trials (PTC124-GD-007-DMD [NCT00592553] [Study 007] and PTC124-GD-020-DMD [NCT01826487] [Study 020]). Data from these studies supported conditional marketing authorization of ataluren for the treatment of nmDMD in ambulatory patients aged ≥ 5 years in Europe and subsequently extended to ≥ 2 years of age based on pharmacokinetic extrapolation from study PTC124-GD 030-DMD.

A detailed description of the chemistry, pharmacology, efficacy, and safety of ataluren is provided in the Investigator's Brochure (IB).

1.2.1 Ataluren-associated increased ribosomal readthrough of premature stop codons

The ability of ataluren to promote ribosomal readthrough of premature stop codons has been evaluated in a wide range of in vivo and in vitro preclinical experiments, including different organ and animal model systems, as well as cell-free and cell-based systems. In particular, preclinical studies in the mdx mouse and the *sapje* zebrafish nmDMD models and human myotubes consistently demonstrate that ataluren increases dystrophin production across key tissues, including skeletal muscle, heart, and diaphragm.

Production of dystrophin from ataluren treatment was also investigated in nmDMD patients in the Phase 2a PTC124-GD-004-DMD study (Study 004) (Finkel 2013). In this trial, 38 nmDMD patients received treatment with ataluren for 28 days. Results from the proof of concept study indicate that ataluren treatment leads to production of full-length dystrophin protein; post-treatment increases in dystrophin were quantified in 61% (23/38) of the patients. The mean change in muscle biopsy dystrophin expression from baseline to Day 28 was 11% ($p=0.008$). In addition, immunohistochemistry experiments indicated the protein was correctly localized to membranes of muscle cells, suggesting functional activity. Myotubes derived from pre-treatment muscle biopsies were cultured in vitro in the presence of ataluren and 100% of the samples showed increases in dystrophin expression. Dystrophin expression was also evaluated in Study 007 in which nmDMD patients were treated with ataluren or placebo. Results from Study 007 were also supportive of an increase in dystrophin levels, consistent with Study 004 results. The increase in dystrophin levels in the two prior clinical studies are limited by the quality of muscle biopsy samples and the use of a non-validated immunofluorescence method of detecting dystrophin protein.

1.3 Risk/Benefit Assessment

Under the current standard of care, nmDMD remains a disease with devastating consequences and bleak prognosis. The progressive and irreversible effects of nmDMD underscore the importance of early intervention with treatments that have the potential to slow physical deterioration and delay the natural course of this fatal disease. While treatment with corticosteroids target the inflammatory component of the disease, additional treatments are needed to address the loss of dystrophin, the underlying cause of the disease.

The mechanism by which ataluren restores dystrophin has been established in comprehensive preclinical studies and supported in clinical evaluations. Moreover, the clinical benefit of ataluren has been demonstrated in two large randomized controlled trials Study 007 and Study 020.

This study is designed to quantitatively evaluate dystrophin protein levels in muscle biopsies from boys with nmDMD who currently have been receiving ataluren for ≥ 9 months. The muscle biopsy technique to be used is less invasive than the standard muscle biopsy and is of relative low-risk to the subject. The use of two highly sensitive validated assays to evaluate dystrophin protein levels will increase the likelihood that each muscle biopsy sample will yield interpretable results. Hence, the study design and the importance of establishing the association of ataluren treatment with dystrophin expression results in a positive risk/benefit.

2 STUDY OBJECTIVE AND ENDPOINTS

2.1 Objectives

2.1.1 Primary Objective

- To assess the levels of dystrophin in ambulatory nmDMD subjects currently being treated with ataluren for ≥ 9 months using a quantitative electrochemiluminescence (ECL) assay

2.1.2 Secondary Objectives

- To assess dystrophin levels/intensity and protein localization by immunohistochemistry

2.1.3 Pharmacokinetic:

- To evaluate the steady state pharmacokinetics (PK) of ataluren

2.2 Endpoints

2.2.1 Primary Endpoint

The primary endpoint is:

- Mean dystrophin levels as measured by ECL

2.2.2 Secondary Endpoints

The secondary endpoint is:

- Levels and localization of dystrophin protein levels as determined by immunohistochemistry

2.2.3 Pharmacokinetic

- PK assessments using sparse sampling and population PK modeling in a separate report. The parameters include Cl/F, V/F, AUC₀₋₂₄, C_{max}, and C_{ave}

3 STUDY DESIGN

3.1 Overall Design

This is a single-site, non-interventional study designed to generate additional data on the effect of ataluren for producing dystrophin protein in nonsense mutation nmDMD subjects. This study will evaluate dystrophin levels from subjects with nmDMD who currently have been receiving ataluren for ≥ 9 months.

Approximately, 6 ambulatory nmDMD male subjects who have been receiving ataluren, dosed daily 10 mg/kg in the morning, 10 mg/kg at midday, and 20 mg/kg in the evening (10, 10, 20 mg/kg), for ≥ 9 months.

The study will have a single visit (Visit 1) which will occur at the site of [REDACTED]. At this visit, inclusion/exclusion criteria, demographics and medical history will be assessed. In addition, blood will be drawn for clinical labs and PK analysis pre-morning ataluren dose. A second blood sample for PK will also be taken 2 hours after morning ataluren dose. The muscle biopsy will also be performed at this visit. Adverse events will be monitored at Visit 1 and by a follow-up phone call approximately 1-week post Visit 1.

3.1.1 Muscle biopsy samples

Muscle biopsies will be performed by appropriately trained staff at [REDACTED]. All subjects will have a physical exam and a history taken and recorded prior to the procedure to assess muscle biopsy locations and determine if there is any intercurrent illness that places a subject at higher risk.

Muscle biopsy of the [REDACTED] and right gastrocnemius [REDACTED] will be performed using an established core muscle biopsy procedure (Gallo 2018). If the [REDACTED] muscle is considered by the investigator to be too small for a muscle biopsy sample, the [REDACTED] muscle may be used. A total of no more than approximately 450 mg of muscle tissue (up to [REDACTED] cores per muscle) will be obtained. Vacuum needle muscle biopsy will be performed using local anesthesia or mild sedation, if needed. All biopsies will be preserved/frozen using standard protocol for ECL and immunohistochemistry (see Section 3.1.2).

The need for conscious sedation will be evaluated on a case by case basis and will be provided by physicians who are credentialed to monitor and provide sedation in an outpatient setting. Following sedation, vital signs will be monitored until the subject returns to pre-sedation baseline values. These techniques are standard of care at [REDACTED] for minor procedures on young patients.

3.1.2 Evaluation of dystrophin levels

Two validated assays, ie, ECL and immunohistochemistry, will be used to assess dystrophin levels. The assays provide slightly different information, and together give a robust analysis.

3.1.2.1 *Electrochemiluminescence assay*

[REDACTED]

Electrochemiluminescence technology provides high sensitivity with a low background. The assay will be optimized and validated by an external contract research organization (CRO). Subject muscle biopsy samples will be shipped to and analyzed for dystrophin levels by a CRO.

3.1.2.2 *Immunohistochemistry assay*

Immunohistochemistry will semi-quantitatively assess dystrophin protein levels and evaluate whether the dystrophin protein is correctly localized to the membrane of the muscle cell, consistent with a functional protein. Dystrophin measured using this assay will be the secondary endpoint. [REDACTED]

[REDACTED] Subject muscle biopsy samples will be shipped to and analyzed for dystrophin levels by a CRO.

3.2 Scientific Rationale for Study Design

The study is designed to generate additional data on the effect of ataluren on promoting the production of dystrophin protein in nmDMD subjects. It is known that even small increases in dystrophin levels can result in milder disease phenotype in nmDMD patients. The levels of dystrophin in patients with Becker muscular dystrophy (BMD) have been reported to be higher than that observed in patients with Duchenne muscular dystrophy (DMD) (Anthony 2014). Consequently, patients with BMD generally have less severe disease compared with those with DMD; BMD patients often show a later onset of disease and slower disease progression (Muntoni 2003, Aartsma-Rus 2006).

As described in Section 1.2.1, the ability of ataluren to promote ribosomal readthrough of premature stop codons has been demonstrated in a range of in vivo and in vitro preclinical assays. In addition, ataluren-associated increases in dystrophin protein levels was assessed in a prior clinical study. Of patients treated with ataluren 10, 10, 20 mg/kg, 55% (8/20) had an increase in dystrophin expression post-ataluren treatment (Finkel 2013). The findings from this study were consistent with ataluren treatment increasing dystrophin levels and indicated that the protein correctly localized to the muscle cell membranes, suggesting functional activity (Finkel 2013).

Assessing dystrophin levels in patients with nmDMD can be challenging due to inherent difficulty in obtaining muscle samples that contain sufficient amounts of intact muscle cells for analysis, as nmDMD muscle, particularly in older patients, are often heterogenous with respect to fibrofatty replacement of muscle.

From prior clinical trial experience, it is anticipated that although levels of dystrophin may increase in nmDMD muscle from baseline following ataluren therapy, the amount of dystrophin will still be low; hence, sensitive assays with good specificity are necessary to evaluate change in dystrophin levels with treatment.

Method of muscle biopsy sampling can also impact results. For example, variability can be introduced by assessing a bilateral muscle sampled from one side of the body before treatment and from the other side after treatment.

This current study is designed to mitigate some of these difficulties.

- Biopsies will be collected from ambulatory nmDMD subjects who have grade 1 or 2 of the Brook Upper Extremity Scale ([Brooke 1989](#), [Connolly 2015](#)) to increase the chance of collecting less heterogeneous muscle tissue.
- A total of no more than approximately 450 mg of muscle tissue (up to [redacted] cores per muscle) will be collected from the [redacted] and [redacted] [redacted]. If the [redacted] muscle is considered by the investigator to be too small for muscle biopsy sampling, the [redacted] muscle may be used.
- Two validated, highly sensitive assays will be employed to measure ataluren-associated increases in dystrophin protein levels and to evaluate whether the protein localizes correctly to the muscle membrane.

3.3 Justification of Dose

Not applicable

3.4 End of Study Definition

The end of the study is defined as completion of the follow-up phone call to assess adverse events (AEs) which occurs approximately 1 week (± 3 days) following Visit 1.

4 STUDY POPULATION

4.1 Overview

4.2 Inclusion Criteria

1. Evidence of signed and dated informed consent/assent document(s) indicating that the subject (and/or his parent/legal guardian) has been informed of all pertinent aspects of the trial.
2. Male sex.
3. Ambulatory (ie, 10m walk/run in <30seconds) and functional grade on the Brooke Upper Extremity Scale of a 1 or a 2.
4. Currently being treated with ataluren 10, 10, 20 mg/kg for ≥ 9 months, with no gap in treatment of >1 month, prior to study entry.
5. Phenotypic evidence of DMD based on the onset of characteristic clinical symptoms or signs (eg, proximal muscle weakness, waddling gait, and Gowers' maneuver) by 6 years of age and an elevated serum creatine kinase (CK). Medical documentation of phenotypic evidence of DMD needs to be provided upon request by the PTC Therapeutics medical monitor.
6. Willing to undergo muscle biopsy.

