7 STUDY ASSESSMENT AND PROCEDURES

7.1 Schedule of Assessments and Study Parameters

Table 1. Schedule of Assessments

Study Procedure	Visit 1 ¹	Follow-up (phone call)	Notes
Week (visit window)		Week 1 (± 3days)	
Informed Consent	X		A signed and dated informed consent must be obtained before conducting any study procedures.
Inclusion/Exclusion	X		
Demographics	X		
Medical History	X		
Physical Exam	X		Full physical exam will be performed.
Clinical Labs	X		Biochemistry, hematology, and urinalysis laboratory assessments.
Height/Weight/BMI	X		
Vitals (HR & BP)	X		Vital signs will include systolic and diastolic blood pressure (BP), pulse rate, and body temperature. The pulse rate and BP determinations will be performed with the subject in a sitting position after a 5-minute rest. Blood pressure will be measured in triplicate and the average will be recorded.
Timed function tests	X		Tests include time to climb 4 stairs, time to descend 4 stairs, time to rise from supine, and time to run/walk 10 meters.
PK blood sampling	X		PK samples will be drawn pre-morning dose and 2 hours post-morning dose. Ataluren plasma concentrations will be analyzed in a population PK model for the estimation of key pharmacokinetic parameters including Cl/F, V/F, AUC ₀₋₂₄ , C _{max} , and C _{ave} .
Muscle biopsy	X		Muscle biopsy will be taken from the [REDACTED] and [REDACTED]. If the [REDACTED] muscle is considered by the investigator to be too small for a muscle biopsy sample, the [REDACTED] muscle may be used.
AE/SAE Monitoring	X	X	
Concomitant medications	X		Treatments, including ataluren, taken one month prior to enrollment and during Visit 1 will be recorded.

Abbreviations: AE, adverse event; AUC₀₋₂₄, area under the concentration curve from time 0 to 24 hours; BMI, body mass index; BP, blood pressure; Cl/F, clearance; C_{ave}, average plasma concentration; C_{max}, maximal plasma concentration; HR, heart rate; PK, pharmacokinetics; SAE, serious adverse event; V/F, volume of distribution

¹ Subjects may have to return to the clinic for up to 3 days for completion of assessments and muscle biopsy.

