6.3 Study Drug Compliance

Since this is a non-interventional study, study drug compliance is not applicable to this study.

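### Inclusion criterion 4 limits how long a treatment gap may be but not when it falls, so a boy just back on ataluren can enter the primary mean with full weight

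*Protocol*

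**What the plan says.** Criterion 4 in protocol section 4.2 reads "Currently being treated with ataluren 10, 10, 20 mg/kg for ≥ 9 months, with no gap in treatment of >1 month, prior to study entry". The synopsis version differs only by a comma. The primary objective (section 2.1.1) is "To assess the levels of dystrophin in ambulatory nmDMD subjects currently being treated with ataluren for ≥ 9 months using a quantitative electrochemiluminescence (ECL) assay".

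Under section 3.1, the eligibility check, both PK samples and the biopsy all belong to one visit. The footnote to Table 1 lets that visit spread over up to 3 days. Table 1 also says of medication history: "Treatments, including ataluren, taken one month prior to enrollment and during Visit 1 will be recorded". Section 6.2 sets the same recording window.

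In the SAP, section 4.3 places in the ITT population every enrolled subject with a valid ECL result, and section 7 bases all efficacy summaries on that population. Section 6.2 puts ataluren use in listings only, and section 6.3 states that "study drug compliance is not applicable to this study". The study is descriptive, with about 6 subjects and no sample size calculation (protocol sections 5.1, 8.1 and 8.1.1).

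**The concern.** The primary result is meant to describe dystrophin in boys on sustained treatment, and criterion 4 is the rule that secures this. It tolerates a gap of up to one month without saying when that gap may occur. A gap that ended many months before the biopsy and one that ended the day before are treated alike, although only the second bears directly on what the biopsy measures.

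The design has little protection against this. There is one biopsy occasion, no pre-treatment sample and no control group, so a low value in a recently interrupted boy cannot be separated by analysis from a low value under continuous treatment. With about 6 subjects, each carries roughly a sixth of the mean.

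**Working it through.** **Step 1: what the criterion admits.** It has three parts: the boy is on ataluren now, his treatment spans at least 9 months, and no single gap exceeded one month. Take a boy with a long treatment history who stopped for 30 days and restarted the day before Visit 1. He is on drug, his history exceeds 9 months, and his gap is not longer than a month. He qualifies. The text does not say whether the 9 months are calendar time since starting or time actually on drug. On either reading this boy passes if his history is long enough.

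**Step 2: whether another rule stops him.**

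| Place | What it tests | Acts on a recent gap? |
|---|---|---|
| Protocol 4.3, exclusion criteria | Biopsy contraindication, other investigational drugs, ventilation, medical conditions | No |
| Protocol 8.2.1 and SAP 4.3, ITT set | Valid ECL result | No |
| Protocol 7.1, Table 1, PK sampling | Timing around one morning dose | No run of prior doses is required |
| Protocol 6.2 and Table 1 | Records ataluren for the month before enrollment and during Visit 1 | Records it only |
| SAP 6.2 | Lists ataluren use | Displays it only |
| SAP 6.3 | Compliance declared not applicable | No |
| SAP 7 to 7.1.2, efficacy | ECL and IHC summaries on the ITT set | No flag, no repeat summary |

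Nothing in the table stops him, so he enters the primary summary like any other subject.

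**Step 3: possible size.** The plan gives no figure to reproduce. The inputs are:

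- n = 6 (protocol 5.1), with each boy contributing one value of equal weight, so one boy carries 1/6 = 17% of the mean.
- A gap of 30 days, the longest a single gap may be, with the biopsy taken before any recovery.
- A half-life h for treatment-related dystrophin off drug. The documents give none, so 7, 14, 28 and 56 days are assumed. Loss is taken as first-order.
- The affected boy would otherwise have had the average treatment-related level.

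Fraction remaining: r = 2^(−30/h). Relative fall in the treatment-related part of the mean: (1 − r)/6.

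| Assumed h (days) | r | (1 − r)/6 |
|---|---|---|
| 7 | 0.051 | 0.949/6 = 0.158 |
| 14 | 0.226 | 0.774/6 = 0.129 |
| 28 | 0.476 | 0.524/6 = 0.087 |
| 56 | 0.690 | 0.310/6 = 0.052 |

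The fall is therefore about 16%, 13%, 9% or 5%.

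**Step 4: from the treatment-related part to the reported figure.** The endpoint is total dystrophin. If a share s of the total mean is treatment-related, the reported mean falls by s × (1 − r)/6. Since s cannot exceed 1, the Step 3 figures are upper values for each half-life. The design has no baseline or control from which to estimate s.

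**The case against.** The best counter-argument is that the gap clause is an ordinary tolerance on ongoing treatment, and that a recent gap would not be hidden. Ataluren use over the relevant month is recorded and listed by subject. With about 6 boys, and with the median, minimum and maximum reported, a careful reader could match a low value to an interrupted boy. Any bias also runs against the drug. This has force, and it means that a reader should not infer that an interrupted boy would pass unnoticed as a poor responder. No responder category is defined, and the listing shows the gap. However, a listing does not decide in advance how such a subject is handled, and the primary mean would still include him unflagged.

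Three stronger readings are tempting, and the documents do not support them.

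- **That his PK samples would not be at steady state.** The PK objective is "To evaluate the steady state pharmacokinetics (PK) of ataluren" and sampling is specified as "PK samples will be drawn pre-morning dose and 2 hours post-morning dose", with no required run of doses beforehand. But the conclusion needs a plasma half-life, which is not given. At assumed half-lives of 2, 6, 12 or 24 hours, 1 − 2^(−24/half-life) gives about 100%, 94%, 75% or 50% of steady state 24 hours after restart. After 72 hours it is about 100%, 100%, 98% or 88%. The population PK analysis is in a separate report and may use actual dosing history.
- **That a month off undoes the effect because 28 days on drug produced one.** Protocol section 1.2.1 reports a mean change of 11% over 28 days of treatment in Study 004. That is a change on drug and says nothing about the rate of loss off drug. The same section says those data are limited by biopsy quality and a non-validated method.
- **That a boy could alternate months on and off.** No total is stated, so 4 of 9 months (44%) off drug would literally pass if the 9 months are calendar time. But such a boy hardly fits the description of being under treatment for that period, and nothing suggests the case is likely. The useful point is only that the basis for counting the 9 months is unstated.

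**Conclusion.** The concern holds for the position of the gap. As written, criterion 4 admits a boy who restarted ataluren just before Visit 1 after up to a month off, and no eligibility, analysis-set or SAP rule acts on that. He could pull down the primary mean for a reason unrelated to sustained treatment.

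How far is not known from the documents. The range of about 16% to 5% of the treatment-related part rests on assumed half-lives of 7 to 56 days, first-order loss, a full 30-day gap, biopsy before recovery and equal weights among 6 subjects. The effect on the reported total is smaller if there is background dystrophin. How often such gaps occur is also unknown. This is an inexpensive tightening worth making before results are seen; it is not a flaw that invalidates the study.

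**What to change.** 1. **Criterion 4, in both the synopsis and section 4.2.** State that the tolerated gap may not fall in the period immediately before Visit 1. The month already recorded under section 6.2 is a practical example, because the data to check it will exist; the sponsor should choose and justify the period. Define interruption so that isolated missed doses do not count. Treatment is left unchanged, and an affected boy's visit is simply scheduled later. In the same clause, say whether the 9 months are calendar time or time on drug. If time on drug is meant, name the source that documents it, since Study 046 records only one month.

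2. **SAP section 7.** Flag any subject with a recorded interruption in that month, and repeat the ECL and IHC summaries without him, alongside the main ITT summaries.

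3. **PK.** Pass the recorded dosing history to the population PK analysis. Automatic exclusion of samples is not justified by what the documents give.

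The cost is an occasional delayed visit, a short amendment to one criterion and one extra summary. The flag uses data already collected. Dropping one of about 6 subjects leaves a very small set, so the repeat summary serves to show how much the result depends on him and does not replace the primary one.
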